10.2 Clinical monitoring

The conduct of the clinical trial will be closely monitored by representatives of GALDERMA R&D and/or Contract Research Organization (CRO) to verify adherence to the clinical trial protocol, ICH-GCP guidelines, and applicable SOPs/study procedures.

The Investigator will allow the CRO / Sponsor's representatives, to have direct access to all clinical trial records, CRFs, corresponding subject medical records, study drug dispensing records, study drug storage area, clinical trial facilities, and any other documents considered source documentation.

The Investigator also agrees to assist the representative if required.

10.3 Data management

The designated CRO will be responsible for activities associated with the data management of this study.

This will include, but not limited to, setting up a relevant database and data transfer mechanisms, along with appropriate validation of data and resolution of queries.

Study sites will enter data directly into an electronic data capture (EDC) system by completing the CRF via a secure internet connection. Data entered into the CRF must be verifiable against source documents at the study center. Data to be recorded directly on the CRF will be identified and the CRF will be considered the source document. Any changes to the data entered into the EDC system will be recorded in the audit trail.

All data management activities will be detailed in a Data Management Plan (DMP).

10.4 Quality assurance / audit / inspection

The clinical trial is conducted under the sponsorship of GALDERMA R&D in compliance with the applicable international and local regulatory requirements as well as applicable ICH guidelines and in accordance with the SOPs for clinical trial conduct and monitoring from GALDERMA and/or the CRO.

At the completion of the study, digital images will be forwarded to the Sponsor according to individual testing facility SOPs.

Audits of clinical trial centers may be conducted by the Sponsor/CRO representatives, and inspection may be performed by Regulatory Authority inspectorates or IRBs/IECs before, during, or after the clinical trial.

The Investigator will allow and assist the CRO /Sponsor's representatives, IRBs/IECs and any regulatory agency to have direct access to all requested clinical trial-related records.

For the audits performed by, or on behalf of, GALDERMA auditors, audit certificate(s) will be provided by Quality Assurance.

10.5 Changes in clinical trial conduct / amendments

10.5.1 Clinical trial conduct

With the exception of eliminating an immediate hazard to a subject, the Investigator should not deviate from the clinical trial protocol or implement any changes without written approval from the Sponsor and prior review and documented approval/favorable opinion from the IRB/IEC of a protocol amendment.

Changes that involve only logistical or administrative changes to the clinical trial protocol are authorized. The Investigator should document and explain any deviation from the clinical trial protocol.

10.5.2 Amendments

The Sponsor may modify the clinical trial protocol at any time for ethical, medical, or scientific reasons.

10.5.3 Attrition

Clinical studies may experience attrition. Subjects will be made aware that they are free to withdraw from the study at any time for any reason, without prejudice. Otherwise, every effort will be made to have subjects complete the study as stated in this protocol, ensuring subject safety and following the provisions of the ICF. Reasons for subject withdrawal may include an AE, SAE, subject's request, protocol violation, lost to follow-up, and other reasons. Subjects lost from the study will be documented on a screening/enrollment log.

If a subject fails to return for a scheduled examination, a representative of clinical site (site representative/study coordinator) will attempt to contact the subject and determine whether the subject has continued to follow study instructions and intends to continue participation in the study. If so, then the subject will be rescheduled to come into the clinic as soon as possible.

If a rescheduled visit is outside of the specified time frame window, this will be recorded in the screening/enrollment log and as a deviation.

If a subject cannot reschedule in an acceptable time frame and completely misses 1 study visit, the subject may be allowed to continue study participation at the discretion of the Investigator and the Sponsor, provided that the subject has continued to comply with study instructions. If the subject is allowed to continue, the missed visit will be noted in the screening/enrollment log and recorded as a protocol deviation. Subjects will not be allowed to miss the week 12 visit.

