11.6	Insurance	69
12	LITERATURE REFERENCE LIST.....	69
13	APPENDICES	72
13.1	Subject Satisfaction Questionnaire.....	72
13.2	Study Drug Acceptability Questionnaire	74
13.3	Dermatology Life Quality Index (DLQI™).....	75
13.4	Children’s Dermatology Life Quality Index (C-DLQI™)	77
13.5	QOL Questionnaire for Face and Trunk Acne (16 years of age and older)	79
13.6	EuroQoL 5-Dimension (EQ-5D-5L)	81
13.7	Fitzpatrick Skin Classification.....	83
13.8	Acne Harmonization Lesion Count	84
CCI		
13.10	Atrophic Acne Scar Counts.....	87
	Protocol Signature Page.....	88

List of Tables

Table 1	Clinical trial schematic	13
Table 2	Schedule of assessments	14
Table 3	Exit Form reasons for discontinuation	31
Table 4	Description and usage of the study drug	32
Table 5	Suspected sensitization - reaction grading	49
Table 6	Suspected sensitization - conclusion	49

SYNOPSIS	
Clinical Trial Title: A Multi-Center Study to Evaluate Subject Reported Outcomes with use of Trifarotene 50 µg/g Cream in the Treatment of Moderate Facial and Truncal Acne Vulgaris	
Short Title: Subject Reported Outcomes with use of Trifarotene 50 µg/g Cream in Subjects with Moderate Facial and Truncal Acne Vulgaris	
Lay Title: Studying the Effects of 50µg/g Cream on Subjects who have Acne	
Clinical Trial phase:	IIIb
Clinical Trial Population:	Subjects with moderate acne vulgaris with facial and truncal acne involvement
Clinical Trial objectives:	The purpose of this study is to evaluate subject reported outcomes with Trifarotene cream.
Clinical Trial design:	Multi-center, open label, single arm study of Trifarotene cream applied once daily in the evening for 24 weeks.
Total number of subjects (Planned):	Approximately 50 subjects will be enrolled in order to obtain 40 subjects at completion.
Number of clinical trial centers (Planned):	CCI [REDACTED]
Region(s) / country(ies) involved (Planned):	United States
Clinical trial duration:	CCI [REDACTED]
Duration of subject participation:	Clinical trial participation for each subject is approximately 24 weeks of study treatment ±3 days. Note: Subjects, upon study completion/early termination, will return to standard of care with their physician.
Key inclusion criteria	
 1. Male or female, 9 years of age and older, at the Screening visit. 2. The Subject has a facial acne CCI [REDACTED]. CCI [REDACTED]

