Analysed variables	
Subject-reported outcomes
 
 DLQI/cDLQI and CompAQ at Baseline and Week 12, 24/Early termination Subject satisfaction questionnaires at Week 12, 24/Early termination EQ-5D-5L at baseline and Week 12, 24/Early termination 
Efficacy variable
 
 CCI [REDACTED] Percent change in the facial IL NI CCI [REDACTED] lesion count from Baseline to Weeks 12 and 24 CCI [REDACTED] Percent change in the trunk IL, NI CCI [REDACTED] lesion count from Baseline to Weeks 12 and 24 Success rate of IGA as the percentage of subjects who achieved an IGA with a score of 1 (almost clear) or 0 (Clear) AND an at least a 2-grade improvement from Baseline at each study visit. Success rate of PGA as the percentage of subjects who achieved a PGA with a score of 1 (almost clear) or 0 (Clear) AND an at least a 2-grade improvement from Baseline at each study visit. 
CCI [REDACTED]
 
CCI [REDACTED]
 
Safety variables
 
 Local tolerability parameters will be assessed at Baseline and each post baseline visits, on all treated areas. CCI [REDACTED] Local tolerance: Raw value at each visit and worst-score across visit, % of Subjects across scores at each post-baseline visit Incidence of adverse events (AESI, SAEs, Death, leading to discontinuation or early termination) 
Other
 
CCI [REDACTED]

Principal statistical method:	
The Intent-to-Treat (ITT) population consists of all enrolled subjects. The Safety population (SAF) consists of the ITT population, who applied at least one dose of treatment.
 
The main objective of this study is to evaluate the subject reported outcomes with trifarotene with 12 and up to 24 weeks of treatment.
 
All variables will be descriptively summarized. All safety endpoints will be summarized based on SAF population and Quality of life and Efficacy endpoints will be summarized

SYNOPSIS	
Clinical Trial Title: A Multi-Center Study to Evaluate Subject Reported Outcomes with use of Trifarotene 50 µg/g Cream in the Treatment of Moderate Facial and Truncal Acne Vulgaris	

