5.6 Procedures/reasons for subject discontinuation

An Investigator may decide to discontinue a subject from the clinical trial for safety reasons.

Although the importance of completing the entire clinical trial should be explained to the subject by the clinical trial personnel, any subject is free to discontinue his/her participation in this clinical trial at any time and for whatever reason, specified or unspecified, and without any prejudice. No constraints are to be imposed on the subject, and when appropriate, a subject may be treated with other conventional therapy when clinically indicated.

When a subject does not complete the clinical trial, he/she will be fully assessed, if such assessment is possible. The procedures designated for the Week 24/Early Termination visit should be completed for all subjects discontinuing the clinical trial and the appropriate CRF page should be completed.

All discontinuations and the reason for discontinuation are to be documented by the Investigator on the Exit Form, and also on the Adverse Event Form for discontinuation due to an AE.

For discontinuation due to an AE, the Investigator should ensure that the subject receives suitable therapy for his/her AE.

A subject who has been enrolled and assigned a kit number cannot be replaced by another subject if he/she discontinues the clinical trial for any reason.

GALDERMA R&D may also decide to prematurely terminate or suspend a subject's participation in the clinical trial.

Potential reasons for discontinuation, as listed on the Exit Form, are defined in Table 3 below:

Table 3 Exit Form reasons for discontinuation

Pregnancy:	Withdraw the Subject from the clinical trial and follow the procedure described in Section 7.2.2.2.5.
Lack of Efficacy:	Investigator judgment only: based on therapeutic/disease-state expectations. If subject opinion only, mark "subject request" and document it in the comment section of the Exit Form.
Adverse Event:	Complete an Adverse Event Form.
Subject Request ^a :	Includes consent withdrawal, subject relocation, schedule conflicts. Explain the reason for withdrawal in the comment section of the Exit Form. If a subject withdraws consent because of an adverse event, the reason for discontinuation should be Adverse Event
Protocol Violation:	Explain the violation in the comment section of the Exit Form.

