9.2 Sample size determination

There is no formal hypothesis to be tested. An estimation approach will be performed. Point estimate and 95% confidence interval will be constructed. Approximately 50 subjects will be enrolled to evaluate the subject reported outcomes (quality of life and satisfaction survey).

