3.4. Treatment Assignment

This is an open label single arm study. All eligible subjects will be assigned to the study drug at Baseline.

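### Protocol 10.5.3 makes staying in the trial after one missed visit depend on compliance and open-label discretion, so less compliant subjects can be lost to later assessment; the bias is probably small and the fix is cheap

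*Protocol*

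**What the plan says.** Protocol 10.5.3 (Attrition) deals with a subject who completely misses one visit and cannot reschedule in time. In that case "the subject may be allowed to continue study participation at the discretion of the Investigator and the Sponsor". A compliance condition is attached to this permission: "provided that the subject has continued to comply with study instructions". No criteria for the discretion are readable. Compliance also enters one step earlier: the site contacts the subject, and rescheduling follows if the subject has kept to the instructions and means to go on. The section ends with "Subjects will not be allowed to miss the week 12 visit" and does not say what happens if that visit is missed.

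The surrounding rules are:

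- **Population.** Protocol synopsis: "The Intent-to-Treat (ITT) population consists of all enrolled subjects".
- **Design.** SAP 3.4: "This is an open label single arm study".
- **Numbers.** Protocol synopsis: "Approximately 50 subjects will be enrolled in order to obtain 40 subjects at completion". Protocol 5.6: "A subject who has been enrolled and assigned a kit number cannot be replaced by another subject".
- **At discontinuation.** Protocol 5.6 asks for the Week 24/ET procedures where that can be done. It describes no later follow-up.
- **Questionnaires.** DLQI/cDLQI, CompAQ and EQ-5D-5L are collected at Baseline, Week 12 and Week 24/ET (Protocol 7.3.2 to 7.3.4). Satisfaction is collected at Week 12 and Week 24/ET (7.3.5). SAP 8.2.1 to 8.2.4 summarise the quality-of-life scores with Week 24 and ET in one row.
- **Missing data.** SAP 6.3 gives LOCF for efficacy endpoints and missing-as-failure (MAF) for binary ones. The opening of SAP Section 8 names IGA, PGA and lesion counts for the observed-case and LOCF analyses.

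**The concern.** Whether a subject is assessed later depends on behaviour after baseline and on a judgement by people who know the treatment and can see the response. Those who leave by this route are not a random subset. Protocol 1.1 supplies the likely direction: it argues that irritation harms compliance and then efficacy, and that better tolerability improves compliance, efficacy and satisfaction. On that reasoning, selecting on compliance tilts the observed results towards subjects who do well.

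The study objective is subject-reported outcomes, and these have only two post-baseline time points. Safety visits also fall at Weeks 1, 4 and 18 (Protocol 3.2). Under the rule, missing one of these can end participation and so cost questionnaires that were still due. MAF protects only the binary success rates, and the readable SAP sections on DLQI, cDLQI, CompAQ and EQ-5D-5L state no imputation. SAP Section 2 says that the results will support regulatory submissions, publications and promotional material, so a systematic tilt that the confidence interval does not show deserves attention.

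**Working it through.** **1. The plan's own figure.** The implied dropout is 1 − 40/50 = 20%, and 40/(1 − 0.20) = 50, so the stated enrolment reproduces. The allowance is 10 subjects for all causes together. There is no power calculation to check: "There is no formal hypothesis to be tested".

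**2. What each missed visit can cost**, if the subject is then removed:

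| Visit missed | Later questionnaires at risk | Partial cover |
|---|---|---|
| Week 1 or 4 | Week 12 and Week 24 | ET enters the Week 24/ET row only |
| Week 12 | Consequence not stated | – |
| Week 18 | Week 24 | ET enters the Week 24/ET row |
| Week 24 | None | – |

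**3. Bias in an unimputed mean.** The observed mean minus the mean of all enrolled equals f × d. Here f is the share unobserved because of the rule, and d is the retained mean minus the removed mean. The documents give neither, so both are assumptions:

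- f = 2% to 10%, that is 1 to 5 of 50 subjects.
- d = 0.2 to 0.5 SD.
- Low end: 0.02 × 0.2 = 0.004 SD.
- High end: 0.10 × 0.5 = 0.05 SD.

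The 95% half-width at n=40 is t(0.975, 39)/√40 = 0.32 SD. The bias is therefore 0.004/0.32 ≈ 1% to 0.05/0.32 ≈ 16% of the half-width.

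**4. Effect of the ET visit.** If a share e of removed subjects attends ET, the unobserved share in the Week 24/ET row falls to f × (1 − e). With e = 0.5 (assumed), the high end becomes 0.10 × 0.5 × 0.5 = 0.025 SD. The ET subjects still contribute a value after shorter exposure, and the documents do not allow that difference to be sized. The Week 12 row gets no such relief.

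**5. Observed-case success rates.** These counts are illustrative and not from the documents.

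- 5 lost, 22 successes among 45: observed case 22/45 = 48.9%, MAF 22/50 = 44.0%. If all 5 lost subjects had succeeded, 27/50 = 54.0%.
- 2 lost, 24 successes among 48: observed case 24/48 = 50.0%, MAF 24/50 = 48.0%.

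MAF is the lower bound, so the success rates have a planned safeguard. The observed-case figures do not.

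**The case against.** The best defence is that the clause is narrow and partly covered. Section 10.5.3 asks for every effort to have subjects complete the study, requires contact and rescheduling, and keeps out-of-window visits as deviations. The clause applies only when a visit is missed altogether. Some of those subjects would be lost under any rule. Those who leave are asked for the full Week 24/ET assessment, which includes the questionnaires and feeds the Week 24/ET row. With one arm there is no imbalance between groups, and with no hypothesis there is no power to lose. All of this stands. It limits the size of the problem but does not remove the selection.

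Three stronger readings are tempting, and the documents do not support them:

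- **That missing Week 12 means removal.** No consequence is stated. The sentence may simply tell sites to secure that visit, which would reduce missing data.
- **That the questionnaires have no protection.** The ET visit gives some. For satisfaction, the SAP analysis text is not visible, so nothing can be concluded about how missing values are handled there.
- **That the bias reaches 0.10 SD.** This needs f = 20% (0.20 × 0.5), which charges all 10 planned losses to this one clause.

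**Conclusion.** The point holds as a design weakness of modest size. As written, 10.5.3 can remove less compliant subjects from later assessment in a trial whose ITT population is everyone enrolled, and Protocol 1.1 gives reason to expect those subjects to do worse. The exposure is confined to removed subjects with no ET visit, Week 12 questionnaires lost after an early removal, and observed-case summaries.

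Under the assumptions above, the shift is small beside the sampling error. It is systematic, however, and no confidence interval reflects it. The documents show a mechanism, not an actual loss, and do not say how many subjects it would affect. The unstated consequence of missing Week 12 is a gap in its own right, because sites could apply the sentence differently. The change is worth making because it costs little, not because the expected bias is large.

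**What to change.** Reword Protocol 10.5.3 along these lines:

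- A missed visit, including Week 12, or non-compliance with study instructions is recorded as a deviation and is not by itself a reason to end participation.
- The subject stays in for all remaining scheduled assessments, except on withdrawal of consent or where the existing discontinuation provisions apply (5.6, and 7.2.2.2.5 for pregnancy). Protocol violation is one of the exit reasons in Table 3 of 5.6, so say expressly that a missed visit or non-compliance alone does not count as one.
- State what follows from a missed Week 12 visit.
- Decisions on study drug stay under the sections that now govern them.

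In the SAP, missed efficacy values follow 6.3. Missed questionnaires are reported as missing, with the number observed shown at each visit.

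The cost is protocol wording and a few more visits. The enrolment target and the analysis methods do not change. Results that include less compliant subjects may look slightly less favourable.

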11 ETHICS AND GENERAL CLINICAL TRIAL CONDUCT CONSIDERATIONS

11.1 Institutional Review Board or Independent Ethics Committee

This study (protocol, ICF and all addenda) will be reviewed and approved by IntegReview IRB. The study will not be activated and subjects will not be consented, receive any study products, or participate in any study procedures until such time as the IRB has approved the protocol and the ICF. In addition, the IRB will review the study before any significant change in the protocol is initiated. After each review, the IRB's approval will be documented in a letter to the Investigator and a copy of the IRB approval letter will be forwarded to the Sponsor.

11.2 Ethical conduct of the clinical trial

This clinical trial will be conducted in accordance with the protocol, the HELSINKI declaration (1964) and subsequent amendments, and the ICH GCP, and in compliance with applicable regulatory requirements.

11.3 Subject information and consent

All subjects who participate in this clinical trial are required to be fully informed about the clinical trial in accordance with GCPs guidelines, federal regulations, HIPAA (if in the US), or applicable local privacy act if in other countries, and guidelines and in accordance with local requirements.

The ICF, Assent Form, HIPAA or other applicable local privacy act), and Photo Consent Form, approved by an IRB/IEC, will be fully explained to the subject.

Prior to enrolment into the clinical trial, the subject and as needed, the subject's parent/legal representative will sign and date the consent form(s), including assent. The Investigator is responsible for maintaining each subject's consent form(s) in the Investigator's site file and providing each subject, and his/her parent legal representative with a copy of the signed and dated consent form(s) including assent.

11.4 Contractual requirements

A contractual agreement will be signed between the Sponsor/CRO and each Investigator/Institution. This document will contain supplementary information, including financial terms, confidentiality, the clinical trial schedule, third party responsibility, and publication rights.

11.5 Data collection and archiving

11.5.1 Data collection

The Investigator must maintain all required records for all subjects. Data for this clinical trial will be recorded in the subject's source documents, subject photographs and on the CRFs provided by the Sponsor. All data should be recorded on the CRFs completely and promptly.

11.5.2 Source documentation

The Investigator must keep accurate separate records (other than the CRFs) of all subject visits, being sure to include all pertinent clinical trial-related information. A statement should be made indicating that the subjects have been included in this clinical trial and have provided signed written Informed Consent and Assent as applicable. All AEs must be thoroughly documented.

Results of any diagnostic tests conducted during the clinical trial should also be included in the source documentation.

11.5.3 Archives

All pertinent data, samples, photographs, correspondence, and reports, the original or amended clinical trial protocol, and all other material relating to the clinical trial will be maintained securely in Sponsor/CRO Investigator/Institution archives for the legally required duration for archiving.

The Investigator/Institution should maintain the essential clinical trial documents as specified in Section 8 of ICH-GCP, and according to the applicable regulatory requirements.

The Investigator/Institution should take measures to prevent accidental or premature destruction of these documents.

If the Principal Investigator retires, relocates, or withdraws from the responsibility of keeping the clinical trial records for any other reasons, custody must be transferred to a person who will accept the responsibility. The Sponsor/CRO must be notified in writing of the name and address of the new custodian.

